## 12.4.1 Parental consent and inclusion of minors

This research will involve adolescent MSM between 15-17 years old. The age range is critical for this research because rates of HIV-related risk behaviors being in adolescence and peak as youth transition into adulthood, and interventions delivered during this time can have the potential to prevent future escalation and

consequences associated with HIV. Given the limited inclusion of youth in HIV biomedical prevention trials, this study has the potential for significant gains for this age group. For participants between the ages of 15 and 17 years, we will request that they are accompanied by a parent and/or legal guardian. These participants will also be asked to assent to participate in study activities.

Similar to prior PrEP trials with youth at the Site, a licensed social worker will serve as the Participant Advocate (JHSPH IRB00007369) and will be present for all study-related procedures if the parent/legal guardian is unable to attend. We will ascertain the extent to which parental permission influences YMSM's willingness to participate in biomedical trials among the subsample who is eligible yet decides not to enroll in the study using in-depth interviews (n=32), as well as those who enroll in the trial (n=16).

### 12.4.2 Assessing for decisional capacity

The informed consent process will include an assessment of each potential participant's understanding of concepts identified by the protocol team as essential to the informed consent decision. For all participants, the research assistant (RA) reviews the informed consent/assent to assess the youth's decisional capacity and ability to provide consent/assent prior to signing, using a 2-step process. First, the RA determines if the person understands the study goals by asking "Can you tell me what this study is about?" In step 2, potential participants will be asked questions designed to assess their capacity to understand, appreciate, reason with, and express a choice about participation in our specific protocol. Participants will be asked to: name things they will be expected to do during the study; explain what they would do if they no longer wished to participate in the study; explain what they would do if they experienced distress during the study; and identify potential risks for participating in the study. For youth who cannot answer these questions, the RA will go back and review the relevant elements of consent with the participant again and repeat the process. Youth who appear not to understand after repeated review will not be enrolled in the study.

#### 12.5 Participant Confidentiality

All study procedures will be conducted in private and every effort will be made to protect participant privacy and confidentiality to the extent possible. The study site will implement confidentiality protections that reflect the local study implementation plan and the input of study staff and community representatives to identify potential confidentiality issues and strategies to address them. In addition to local considerations, the protections described below will be implemented at all sites.

All laboratory specimens, questionnaires, evaluation forms, reports, and other records will be identified by a coded number and initials only, to maintain participant confidentiality. All records with personally-identifying information will be kept in a locked, limited access area (such as a locked file cabinet). All computer entry and networking programs will be done with coded numbers and initials only. Clinical information will not be released without written permission of the participant (and parent or legal guardian, when applicable), except as necessary for monitoring by the iTECH MC or NICHD.

All study-related information will be stored securely at the study site. All participant information will be stored in locked file cabinets in areas with access limited to study staff. Data collection, process, and administrative forms, laboratory specimens and other reports will be identified by a coded number only, to maintain participant confidentiality. Forms, lists, logbooks, appointment books and any other listings that link participant ID numbers to other identifying information will be stored in a separate, locked file in an area with limited access. All local databases will be secured with password-protected access systems. Participants'

study information will not be released without their written permission, except as necessary for review, monitoring, and/or auditing by:

- Representatives of the US Federal Government, including the US Food and Drug Administration (FDA), the US Office for Human Research Protections (OHRP), NIH, and/or contractors of the NIH
- Representatives of the Sponsor
- DREAM IND Regulatory Program
- Site IRB
- JHU legal representatives and other JHU staff

## 12.5.1 Certificate of Confidentiality

This research specifically targets a vulnerable population, children (YMSM ages 15-17). We will take every available step to minimize the risk of identifying/linking data being subpoenaed, stolen, or inadvertently released. First, the iTech has obtained a Certificate of Confidentiality from the NIH. Second, all research staff members are required to complete ethical clearance certification regarding protection of human's subjects through their relevant IRBs. Third, all studies will have documented procedures to safeguard against the risk of the linking information being stolen by keeping such information in a locked spaces to which only essential study personnel who have completed CITI certification for human subjects research ethics training (http://citiprogram.org) will have access.

Per Section 2012 of the 21st Century Cures Act as implemented in the 2017 NIH Certificates of Confidentiality Policy, all ongoing or new research funded by NIH as of December 13, 2016 that is collecting or using identifiable, sensitive information is automatically issued a CoC. As noted on the NIH website (http://grants.nih.gov/grants/policy/COC/faqs.htm#187), a Certificate of Confidentiality will help the research team "...avoid compelled 'involuntary disclosure' (e.g., subpoenas) of names and other identifying information about any individual who participates as a research subject (i.e., about whom the investigator maintains identifying information) during any time the Certificate is in effect."

## **12.6** Special Populations

This section outlines considerations made for the inclusion or exclusion of special populations in this study.

## 12.6.1 Women

Only healthy male volunteers with a history of recent RAI will be included in this study, as the rationale for use of the enema as rectal microbicide is based on established behaviors in MSM related to pre-RAI enema use. The enema use behaviors in women are far less well studied and, where data do exist, it suggests women do not use enemas in the same manner as MSM. This selected MSM population also comprises a large portion of the target population for rectal microbicide use in the United States.

## 12.6.2 Children

The NIH has mandated that children be included in research trials when appropriate. This study meets *Justifications for Exclusion* criteria for younger children as set forth by the NIH. Because of the need to understand douching as a potential PrEP option for adolescents, this study plans to enroll adolescents defined as 15 -24 years old.

#### 12.7 Compensation

Pending IRB approval, participants will be compensated for their time and effort in this study, and/or be reimbursed for travel to study visits, child care, and time away from work according to site's practice. Reimbursement amounts will be specified in the site's informed consent form.

Participants will also receive a per diem for food and round trip fare to the study site (\$110 total), as well as having their hotel covered by study.

Participants who do not complete visit 4 will receive a pro-rated amount for visits completed (at \$25 per visit completed). All participants who participate in the study will be offered the opportunity to participate in an indepth interview. This is regardless of which visit is completed. Participants will be provided food and transportation at each study. If participants need to stay overnight for a visit (for example, between visit 3 and 4), the study will also cover a one night's hotel stay.

### 12.8 Communicable Disease Reporting

Study staff will comply with all applicable local requirements to report communicable diseases including HIV identified among study participants to local health authorities. Participants will be made aware of all reporting requirements during the study informed consent process.

## 12.9 Access to HIV-related Care

## 12.9.1 HIV Counseling

HIV test-related counseling will be provided to all potential study participants who consent to undergo HIV screening to determine their eligibility for this study. Testing will be performed in accordance with the algorithm in Appendix II. Counseling will be provided in accordance with standard HIV counseling policies and methods at the participating study site and additionally will emphasize the unknown efficacy of the study products in preventing HIV infection. In accordance with NIH policies, participants must receive their HIV test results to take part in this study. Referral for additional counseling related to testing or diagnosis will occur if needed or requested by the participant.

## 12.9.2 Care for Participants Identified as HIV-infected

Participants will be provided with their HIV test results in the context of post-test counseling. Per site SOPs, participants found to be HIV-infected will be referred to available sources of medical and psychosocial care and support, and local research studies for HIV-infected adults.

#### **12.10 Study Discontinuation**

This study may be discontinued at any time by NICHD, Sponsor, US FDA, the OHRP, or site IRB.

## **13. PARTICIPANT MANAGEMENT**

#### **13.1** Tracking Participants / Follow-up

Participants will be contacted to schedule their visits and IDIs. Multiple contact methods will be used for participants to remind them about their scheduled visits, (e.g., phone calls, alternative email addresses, text messages, Facebook/other social media accounts). Participants will be asked whether or not messages can be left for any phone numbers they provide. They will be informed that messages will not contain any information regarding the nature of the project.

### 13.2 Intervening on "Social Harms"

All sites have specific policies governing the treatment of human subjects. These policies specify that medical and psychological assistance will be available in the immediate environment in the event a participant should experience any adverse reactions resulting from study procedures.

While participants will be informed that they may refuse to answer any question at any time, responses or reactions to certain questions may indicate distress on the part of the participants. If at any time during the study, a participant divulges that he or she is at risk for harm, including but not limited to being abused or experiencing violence, if harm is suspected or likely, or if the participant states he or she is suicidal/homicidal, measures will be taken to ensure his or her safety. Reporting will be done as appropriate to the situation and the legal statutes, including reporting to child protection agencies or other appropriate agencies and referrals will be provided to appropriate support, counseling or treatment resources.

#### **13.3** Criteria for Premature Study Discontinuation

The principal investigator has the authority to withdraw any participant at any time if it their opinion it would be in the best interest of the participant. The participant will be informed of this withdrawal and explained the rationale. Withdrawal will be documented in the study tracking system.

Subjects will be prematurely discontinued from the study if any of the following occurs:

- a. The subject withdraws consent/assent;
- b. The study is cancelled by the *NIH* (or *iTech*, or other administrative entity);
- c. The study is cancelled for other administrative reasons; or
- d. Death of the subject.

Participants may end their participation in the study at any time. No further data collection will occur from the date the decision is made to permanently discontinue the subject from the study. Participants who experience distress during the survey can access our list of community referrals or contact the research staff using the information provided to the participant during the consent/assent process. Any unexpected adverse events that meet the New Safety Information reporting criteria will be immediately reported to the UNC-CH IRB and the respective sites' IRBs if applicable. All study activities will halt pending UNC-CH IRB review and recommendations if necessary. If a participant withdraws from the research, all data collected will be immediately destroyed and will not be used in subsequent analysis.

If a participant withdraws or is removed from the study, the DREAM Study Stop Form will be completed.

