# Table 10: Visit 3 – Dosing Visit (Day 1)

 Safety labs will be drawn prior to dosing and initiation of any specimen collections.

\* Post-dose PK collection time points are approximate. Every effort will be made to adhere to the timeline, however, due to logistics, timing will not be exact and specimen collections may be missed (i.e. during biopsy collection). \*\*Biopsies taken depend on participant's individual sampling schedule

\*\* Biopsies and post-dose rectal fluid collection taken depend on participant's individual sampling schedule

\*\*\* Microbiome and rectal fluid collection should be done prior to dosing or enema administration and microbiome collection should precede rectal fluid collection.

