## 6.7 Visit 6- Termination Visit- 96 hour (Day 5 + 3 days)

The Termination Visit ideally should occur at 96 hours (+3 day window) for all participants. The term visit should be at least 24 hours after the last scheduled biopsy. This visit will serve as the participant's study termination.

During their Termination Visit, participants will complete an exit in-depth interview (IDI) that will explore their experiences participating in the study, user-centered suggestions for product design and delivery, factors influencing product use in the future, and suggestions to maximize YMSM's engagement in future biomedical trials, including how to overcome perceived barriers and challenges based on their experiences. The IDI will be conducted using video-conferencing by a trained interviewer located at the University of Pennsylvania.

If a participant withdraws from study participation early or is withdrawn early from study participation by the study team, they will be asked to come in for an Early Termination Visit and the all the activities conducted at the Termination Visit will also be conducted for the Early Termination Visit.

Component	Procedure/Analysis	
Administrative	
 
Review/update demographic and locator information
 
Review STI risk reduction counseling and provide condoms
 
	
Clinical	
 
Review/update medical history
 
Review/update concomitant medications
 
Review any available test results
 
Complete AE assessment
 
Symptom-directed physical exam as needed
 
Obtain vital signs (HR, BP, Temp)
 
Collect blood specimens for:
 
	
Safety Labs and STI Screening: blood	
 
Collect blood specimens for:         
 
CBC with differential
 
CMP
 
HIV-1 antigen/antibody 4th generation testing (confirmatory tests as needed) *
 
Syphilis Testing (confirmatory test as needed) *
 

 
 
 
	
Safety Labs and STI Screening: urine and rectal	
 
Collect urine sample for GC/CT (NAAT) *
 
Collect rectal swab for GC/CT (NAAT) *
 
Collect swab for HSV, if indicated *
 
	
Other Specimens (rectal fluid, etc.)	• Collect specimens as appropriate/indicated (if the participant is willing) *	
Behavioral	Completion of exit in-depth interview	

Activities to take place at the Termination Visit include: **Table 12: Termination Visit** 

\*If indicated and/or per local standard of care.

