#### Table 13: Interim Visit

#### 6.10 Participants Who Withdraw or Are Withdrawn from the Study

If the participant withdraws or is withdrawn from the study after receiving study product, an Early Termination Visit will be conducted, if possible. The protocol principal investigator in consultation with the site investigator will determine if research participants who fail to complete all biopsy collection sessions should be replaced. Replacement subjects would be assigned the same sampling schedule as the subject they are replacing.

Any participant with quantifiable plasma TFV/FTC or PBMC TFV-DP/FTC-TP concentrations at the Enrollment Visit (Visit 2) will be replaced.

Participants with quantifiable plasma tenofovir/emtricitabine concentrations at Visit 2 will not proceed to the tenofovir douche administration and pharmacokinetic sampling portion of the protocol. These participants may continue to participate in the In-Depth Interview portion of the protocol.

PBMC TFV-DP/FTC-TP concentrations will be measured periodically. Participants with quantifiable TFV/DP/FTC-TP concentrations may continue to the TFV douche administration and pharmacokinetic sampling portion of the protocol, but may be replaced once the PBMC TFV-DP/FTC-TP results are available.

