### 7.3 Criteria for Early Termination of Study Participation

Participants may voluntarily withdraw from the study for any reason at any time. The site investigator also may withdraw participants from the study to protect their safety and/or if they are unwilling or unable to comply with required study procedures. Participants also may be withdrawn if the study sponsor, government or regulatory authorities (including the Office of Human Research Protections), NICHD or site IRBs terminate the study prior to its planned end date. Every reasonable effort is made to complete a final evaluation of participants who withdraw or are withdrawn from the study prior to completing follow-up. Study staff members will record the reason(s) for all withdrawals in participants' study records.

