#### 9.7 Missing Data

All reasonable efforts will be made to obtain complete data for all participants; however, missing observations will occur due to missed visits, participants lost to follow-up, or noncompliance. Research participants who fail to complete dosing and evaluations relevant to all study product doses for any reason may be replaced at discretion of the study site investigator after consultation with the Sponsor. Data for PK and distribution will be required of all periods of the study or the research participant will be replaced.

Several procedures will be used to conduct data analysis when data for either outcomes or covariates are missing. The first step will be to assess the extent and pattern of missing data. If data are missing for only a few cases, then data analysis will be conducted only on study participants with complete data. However, when such a strategy would result in loss of data from a substantial proportion of participants, or if this approach would lead to biased or inaccurate results, then some form of imputation will be performed. The form of imputation used will depend on the nature of the data that are missing. For example, data that are collected repeatedly might be imputed using the "last value carried forward" method; and in some instances, interpolation between neighboring points might also be used. When the primary endpoint is missing, one data analysis will be conducted using only cases with the endpoint. Subsequent analysis will be done where missing endpoints are imputed. Hot-deck imputation or regression imputation may also be used in this context.

As previously noted, all available data will be used for safety purposes. All available data will also be used for descriptive purposes. Formal statistical comparisons between study products, however, must necessarily be limited to subjects who complete use of study products. The between-product comparisons are critical to allow the use of the data in this study to guide future rectal microbicide development. Accordingly, the protocol principal investigators in consultation with the site investigators will determine if research participants who fail to complete all PK collection sessions should be replaced. Replacement subjects would be assigned the same sampling schedule as the subject they are replacing.

The familywise error rate corrections will be used to adjust for multiple comparisons.

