### **10.2** Source Documents and Access to Source Data/Documents

All study sites will maintain source documents and data in accordance with *Requirements for Source Documentation in DAIDS Funded and/or Sponsored Clinical Trials:* (http://www.niaid.nih.gov/LabsAndResources/resources/DAIDSClinRsrch/Documents/sourcedocpolicy.pdf).

Each investigator will maintain and securely store complete, accurate, and current study records throughout the study. Per US regulations, for all investigational products tested, the investigators will retain all study records on site for at least two years following the date of marketing approval for the study product for the indication in which it was studied. If no marketing application is to be filed or if the application is not approved, the records must be retained until two years after the investigation is discontinued and the US FDA is notified.

Study records must be maintained on site for the entire period of study implementation. Thereafter, instructions for record storage will be provided by Sponsor. No study records may be moved to an off-site location or destroyed prior to receiving approval from both NICHD and Sponsor.

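### Section 13.3 orders destruction of all data from a participant who withdraws, which contradicts the safety-analysis, record-retention and early-termination rules and can erase primary-endpoint adverse events

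*Combined protocol and SAP*

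**What the plan says.** Section 13.3 (Criteria for Premature Study Discontinuation) has two data rules. On data already held: "If a participant withdraws from the research, all data collected will be immediately destroyed and will not be used in subsequent analysis". On data still to come: "No further data collection will occur from the date the decision is made to permanently discontinue the subject from the study". The one sentence there about adverse events concerns reporting unexpected events to the IRB; it keeps nothing for analysis.

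Other sections say otherwise:

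- Section 9.7 (Missing Data): "As previously noted, all available data will be used for safety purposes".
- Section 10.2 (Source Documents) sets a retention period and adds: "No study records may be moved to an off-site location or destroyed prior to receiving approval from both NICHD and Sponsor".
- Section 9.6 (Data Analysis, Safety) plans a separate table of adverse events that led to discontinuation.
- Section 6.10: "If the participant withdraws or is withdrawn from the study after receiving study product, an Early Termination Visit will be conducted, if possible".
- Section 6.7 asks people who withdraw, or are withdrawn, to attend an Early Termination Visit, and says that the "activities conducted at the Termination Visit will also be conducted for the Early Termination Visit".
- Section 7.3: "Every reasonable effort is made to complete a final evaluation of participants who withdraw or are withdrawn from the study prior to completing follow-up".

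Section 2.2 makes Grade 2 or higher clinical and laboratory adverse events a primary endpoint. The plan enrols 16 people.

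**The concern.** Site staff cannot obey all of these provisions. Once data have been destroyed under 13.3, the all-available-data rule in 9.7 has nothing left to act on for that participant. Immediate destruction cannot wait for the two approvals in 10.2. An adverse event that made someone withdraw cannot appear in the 9.6 table if the record is gone. A closing visit cannot be held, or used, if collection stops at the decision date and everything collected is destroyed.

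The primary safety endpoint is what is exposed. The schedule in Appendix I places CBC and CMP at Visits 1, 3 and 6 only. Section 6.5 has the Visit 3 baseline safety samples taken before the douche, and a footnote to Table 10 says "Safety labs will be drawn prior to dosing and initiation of any specimen collections". Visit 6, or the Early Termination Visit that stands in for it, therefore holds the only scheduled CBC and CMP after dosing. Losing that visit for a withdrawing participant loses the scheduled laboratory half of the endpoint.

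If people with an adverse event are more likely to withdraw, the observed rate is biased downward. Replacement, which is discretionary under 4.4, 6.10 and 9.7, restores the number of participants but not the lost event.

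**Working it through.** **Inputs.** n = 16 and the 81% detection figure at a true rate of 10% (Section 9.6, Safety); exact 95% confidence intervals for binomial endpoints (Section 9.6); 90% retention target (Section 4.4). The documents give no probability that a participant with an adverse event withdraws. Call it w; every value of w below is an assumption.

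**Step 1: reproduce the plan's figure.** P(at least one of 16) = 1 − (1 − p)^16. At p = 0.10 this is 1 − 0.9^16 = 0.815, which matches the stated 81%. At p = 0.01 it is 0.149, which matches the stated figure of under 15%.

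**Step 2: effect on counts, with exact (Clopper-Pearson) 95% intervals.** Suppose two of 16 have a Grade 2 or higher event.

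| What happens | Analysed | Rate | 95% CI |
|---|---|---|---|
| Nobody withdraws | 2/16 | 12.5% | 1.6% to 38.3% |
| One of the two withdraws | 1/15 | 6.7% | 0.2% to 31.9% |
| Same, with an event-free replacement | 1/16 | 6.3% | 0.2% to 30.2% |
| Both withdraw | 0/14 | 0% | 0% to 23.2% |
| Same, with two event-free replacements | 0/16 | 0% | 0% to 20.6% |

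**Step 3: effect on the chance of seeing any event.** Assume that a participant with an event withdraws with probability w, that nobody else withdraws, and that each person lost is replaced until 16 are analysed. The rate among those analysed is q = p(1 − w)/(1 − pw), and the detection probability is 1 − (1 − q)^16. Without replacement, each of the 16 contributes a recorded event with probability p(1 − w), and the detection probability is 1 − (1 − p(1 − w))^16. At p = 0.10:

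| w (assumed) | q with replacement | P(≥1 event), replaced | P(≥1 event), not replaced |
|---|---|---|---|
| 0 | 10.0% | 81% | 81% |
| 0.10 | 0.090/0.990 = 9.1% | 78% | 78% |
| 0.25 | 0.075/0.975 = 7.7% | 72% | 71% |
| 0.50 | 0.050/0.950 = 5.3% | 58% | 56% |

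**Step 4: losses unrelated to adverse events.** A 90% target implies 16 × 0.10 = 1.6 participants lost. Losing one gives 1 − 0.9^15 = 0.794; losing two gives 1 − 0.9^14 = 0.771. Without a link between events and withdrawal, the harm is modest.

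**Step 5: who is covered.** The destruction sentence speaks only of a participant who withdraws. The sentence after it, on completing a stop form, also mentions removal. Section 7.11 has *Withdrawal* in its heading but describes termination by the protocol after a study-associated Grade 2 or higher event. Self-initiated withdrawal is clearly covered; termination by staff may or may not be. On the wide reading w would be 1 for study-associated events, and none of them would reach the analysis.

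**The case against.** The case on the other side has five parts.

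- **Section 10.2 is a barrier to destruction, and 9.7 is the analysis rule, so the data might in practice survive.** They might, but only if someone decides that 13.3 gives way, and no text says so. These sections are part of the contradiction and do not resolve it. Adverse events do also appear in monthly reports and expedited reports, and those already issued would survive; they are not the analysis dataset.
- **The sentence looks carried over from a survey study.** Its paragraph refers to distress during a survey and to an IRB other than the single IRB of record named in 12.1. That may explain its origin, but it still says all data.
- **The exposed group may be narrow.** Read literally, participants terminated under 7.11 are removed and do not withdraw, so destruction would not be triggered for them. What remains is people who leave by their own choice, within a follow-up that ends about 96 hours (+3 days) after one dose. This limits how often the rule would bite, and it also removes the conflict with the 9.6 table for 7.11 terminations. It does not help those who leave because of an event.
- **The values of w are assumed, full replacement is assumed, and the retention target includes loss to follow-up, which 13.3 does not address.** This is right. The figures show possible size and are not a forecast.
- **The closing-visit provisions are best-effort.** They are, but asking for a visit still conflicts with a bar on further data collection.

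**Conclusion.** The concern holds. As written, 13.3 requires immediate destruction and non-use of all data from a withdrawing participant, has no safety exception, and cannot be carried out alongside 9.7, 10.2, or the closing-visit provisions of 6.7, 6.10 and 7.3. This follows from the text alone.

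The numerical size depends on how many affected participants withdraw, which the documents do not give. It ranges from a loss of two to four percentage points in detection probability when one or two losses are unrelated to adverse events, to a loss of about 23 points (81% to 58%) if half of those with an event withdraw and are replaced. With so few participants, one or two erased events change the reported safety result, and destroyed data cannot be recovered. This should be fixed before any participant withdraws.

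**What to change.** 1. In 13.3, delete the destruction sentence. State that data recorded up to withdrawal, and data from any Early Termination Visit the participant agrees to, are kept and included in the safety analysis.
2. Reconcile the 13.3 sentence on ending data collection with 6.7, 6.10 and 7.3.
3. Say whether the 13.3 data rule applies to participants removed by staff, including those terminated under 7.11.
4. In 9.7, state that every dosed participant, including anyone later replaced under 4.4, 6.10 or 9.7, stays in both numerator and denominator of the safety analysis.
5. Check that the consent form agrees. Its pages are not in the reviewed copy, so whether it promises destruction is unknown.

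The cost is a short text amendment to 13.3 and 9.7, with no added procedures. If the consent form does promise destruction, a consent revision and IRB review would also be needed.
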